The Phase 2 immunotherapy regimen will include 1 priming dose of the α DC1 vaccine and 3 booster doses of the α DC1 vaccine combined with CKM. Each dose of vaccine, whether priming or booster, will include 1 intranodal (3M cells) and 1 intradermal (3M cells) injection. Phase 1 includes only the priming vaccine dose and 1 cycle of a booster dose + CKM.

Each booster vaccine dose (booster cycles 1-3) will be followed by 4-days of systemic CKM which is comprised of intravenous (IV) IFN α (dose-escalation in Phase 1 only: 5-20 MU/m 2) once a day for 4 days; IV rintatolimod (short-half-life TLR3 ligand) 200 mg on Wednesday and Friday only of the CKM regimen; and oral celecoxib 200 mg twice a day for all 5 days.

In order to avoid overlap between experimental immunotherapy and potential adjuvant chemotherapy (which can be clinically indicated as a part of standard care in a subset of patients), the experimental treatment may be interrupted after each cycle to allow adjuvant chemotherapy that may be done for each patient's clinical care, not as part of this research study. If clinically indicated any cycle of adjuvant chemotherapy may start a minimum of 5 days after completion of a cycle of immunotherapy and recovery from any potential side effects. The following cycle of immunotherapy may start at least 5 days after the completion of chemotherapy and after recovery from acute side effects of chemotherapy.

Timing of the experimental treatment:

- Priming cycle (vaccine alone): 6 to 16 weeks after surgery (target: 8 weeks)
- Booster cycle 1 (vaccine plus CKM): 4 to 12 weeks after priming cycle (target: 4 weeks)
- Booster cycle 2 (vaccine plus CKM): 4 to 12 weeks after booster cycle 1 (target: 4 weeks)
- Booster cycle 3 (vaccine plus CKM): 4 to 12 weeks after booster cycle 2 (target: 4 weeks)

The primary endpoint will be time to tumor progression/recurrence on CT or MR imaging. Secondary endpoints will be immunologic response markers.

UPCI #: 12-110

Version Date: 03-18-2016

The schemas for the trial are located in Sections 5.1 and 5.2.

TABLE OF CONTENTS

SCHEMA.....	2
LIST OF ABBREVIATIONS.....	6
1. OBJECTIVES	8
1.1 Primary Objectives.....	8
1.2 Secondary Objectives.....	8
2. BACKGROUND	8
2.1 Tumor Immunogenicity in Malignant Peritoneal Mesothelioma.....	8
2.2 Tumor Immunogenicity in Colorectal Adenocarcinoma with Peritoneal Carcinomatosis.....	10
2.3 Tumor Immunogenicity in Appendiceal Adenocarcinoma with Peritoneal Carcinomatosis.....	11

ACE inhibitor	angiotensin-converting-enzyme inhibitor
AE	Adverse event
ALP	Alkaline phosphatase
ALT (SGPT)	Alanine aminotransferase
ANC	Absolute neutrophil count
AST (SGOT)	Aspartate aminotransferase
BUN	Blood urea nitrogen
cc	cubic centimeters
CC score	Completeness of Cytoreduction score
CEA	Carcinoembryonic antigen
cGMP	current good manufacturing practice
CKM	chemokine modulation
CRS	Clinical Research Services
CT	Computed tomography
CTCAE	Common Toxicity Criteria for Adverse Events
CTLs	Cytotoxic T-Lymphocyte
CTRC	Clinical & Translational Research Center
DLT	Dose-limiting toxicity
DSMB/DSMC	Data Safety Monitoring Board/ Data Safety Monitoring Committee
ECG	Electrocardiogram
FDA	Food and Drug Administration
GM-CSF	granulocyte-macrophage colony stimulating factor
HSA	human serum albumin
IB	Investigator's brochure
IFN α	interferon alpha
ILCI	intensive locoregional chemotherapy and immunotherapy
IN	intranodal
IND	Investigational new drug
IP	intraperitoneal
IRB	Institutional Review Board
ITC	Immunotransplantation Center
IV	intravenous
MDSC	myeloid-derived suppressor cells
Mg	milligrams
mL	milliliter
MRI	Magnetic resonance imaging
MTD	maximum tolerated dose
MU	million units

NCI	National Cancer Institute
NK cells	natural killer cells
NSAID	non-steroidal anti-inflammatory drug
OS	Overall survival
OvCa	ovarian cancer
PBMC	Peripheral blood mononuclear cell
PET	Positron emission tomography
PFI	progression free interval
RP2D	Recommended Phase 2 dose
PS	Performance status
PTT	partial thromboplastin time
RECIST	Response Evaluation Criteria in Solid Tumors
RNA	Ribonucleic acid
SAE	Serious adverse event
SOC	Standard of care
TILs	tumor infiltrating lymphocytes
TLR	toll-like receptor
TTP	Time to progression
ULN	Upper limit of normal
UPCI	University of Pittsburgh Cancer Institute
USP	United States Pharmacopeia
UV	ultraviolet
αDC	alpha dendritic cell

1. OBJECTIVES

1.1 Primary Objectives

Preliminary data from our laboratory indicate that autologous antigen-loaded α DC1 vaccines induce highly-effective tumor-specific CD8 $^{+}$ CTLs that express defined chemokine receptors, CCR5 and CXCR3.¹⁻³ We have also demonstrated that IFN α and poly-I:C enhance local production of relevant chemokines CCL5/RANTES and CXCL10/IP10 that are able to attract the CCR5- and CXCR3-expressing CTLs selectively to tumor lesions, rather than in marginal healthy tissues. Furthermore, the above factors suppress local production of undesirable chemokines (CCL22) that attract immunosuppressive T_{reg} cells.⁴ In addition, studies have demonstrated a correlation between the density of infiltrating effector T cells and long-term outcomes in malignant peritoneal mesothelioma^{5,6} and colorectal cancer^{7,8}.

In this Phase 1/2 clinical trial, we will test the effectiveness of the treatment of patients with peritoneal surface malignancies, including but not limited to malignant peritoneal mesothelioma (MPM) and peritoneal carcinomatosis (PC) from appendiceal and colorectal primary tumors, using autologous α DC1 vaccines combined with a systemic chemokine modulation regimen, consisting of celecoxib, IFN α , and TLR3 ligand as a component of adjuvant therapy. We anticipate that the resulting tumor-selective modulation of the peritoneal chemokine environment will promote the entry of spontaneously-occurring and α DC1-induced effector-type T (*eff*) cells into tumor, and limit the influx of undesirable regulatory-type T (*reg*) cells.

Our primary objective is to test whether our combined immunotherapy regimen (α DC1 vaccines + CKM) is safe and whether it can prolong time-to-progression (TTP) in patients with peritoneal surface malignancies after optimal CRS + HIPEC with or without adjuvant chemotherapy.

1.2 Secondary Objectives

- To estimate overall survival (OS).
- Perform correlative studies to characterize sequential immune response changes by quantitative measures of immune cellular phenotypes and chemokine patterns in peripheral blood. These results will be correlated with TTP, PFS, and OS in attempt to predictive markers of the clinical benefit.

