Studies have shown that patients with malignant pleural mesothelioma who demonstrate robust anti-tumor immune responses survive longer. Increased CD8+ tumor-infiltrating lymphocytes (TILs) are associated with lower incidence/burden of mediastinal lymphadenopathy, higher numbers of apoptotic tumor cells in tumor tissue, as well as improved progression-free and overall survival after surgical resection, with or without neoadjuvant chemotherapy. This suggests that stimulation of CD8+ TILs is a potential therapeutic strategy. In fact, patients receiving neoadjuvant chemotherapy with cisplatin/pemetrexed combination demonstrate higher CD8+ TILs than those receiving other chemotherapy regimens, lending credence to this being the most efficacious regimen in randomized trials.^{5,6} However, the immune cell population of mesothelioma strongly favors a suppressive environment, with heavy infiltration of CD4+CD25+Foxp3 regulatory T cells (T_{regs}), and an absence of CD1 α + DCs, which might explain the lack of tumor kill despite high levels of effector T cells. This immunosuppressive environment must be modulated to improve immunotherapeutic efficacy.¹⁵

Intra-peritoneal delivery of tumor-lysate pulsed DCs prior to intra-peritoneal tumor implantation of mouse mesothelioma cell line AB1 prevents tumor engraftment, halts mesothelioma progression and provides long-term protection against tumor re-challenge. In an adjuvant setting, this immunotherapy demonstrates a better outcome when delivered early after AB1 tumor implantation, when tumor burden is less. Mice receiving DC vaccine have higher AB1 cell lysis (chromium release assay) and higher IFN γ production from splenocytes (ELISPOT assay), suggesting an overall increased CTL activity. Adoptive transfer of CD8+ T cells, isolated from splenocytes of immunized mice, into non-immunized AB1 tumor bearing mice improves survival.¹⁶ A small Phase 1 clinical trial (10 patients) in patients with mesothelioma was performed to assess toxicity and feasibility of clinical grade DC vaccine immunotherapy and tumor response to immunotherapy. DCs were pulsed with autologous tumor lysate, matured ex-vivo, and then administered intradermally and intravenously to select malignant pleural mesothelioma patients with epithelioid histology that demonstrated partial response or stable disease following CRS + cisplatin chemotherapy. DC immunotherapy was well tolerated and

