appeared to elicit an immunologic response (positive DTH skin test, increased inflammatory cells in skin biopsies at site of vaccination, increased antitumor T cells in blood) and some clinical response by RECIST (of 10 patients, 6 had progression, 1 had stable and 3 had partial response), however no survival benefit was noted.¹⁷ Recent evidence indicates that chemotherapeutic agents can induce specific immune responses, thereby improving therapeutic outcomes. Chemotherapy induced dead tumor cells may release “danger signals” that induce DC maturation with subsequent CTL activation. In a murine model of mesothelioma, gemcitabine has been shown to increase antigen presentation to CD8+ T cells. Vaccination of these tumor-bearing mice following gemcitabine therapy resulted in a marked decrease in tumor growth and increased survival compared with vaccination without gemcitabine.¹⁸ Similarly, certain cytotoxic drugs like cisplatin have been shown to increase the sensitivity of tumor cells to immune-mediated attack.¹⁹

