Study treatment will consist of one priming dose of DC vaccination followed by 3 booster cycles of DC vaccine + chemokine modulation regimen (CKM), cycles 1-3. The booster vaccine is administered on Monday followed by 4 days of the CKM regimen (Tuesday – Friday).

Timing of the experimental treatment:

- Priming cycle: 6 to 16 weeks after surgery (target: 8 weeks)
- Booster cycle 1: 4 to 12 weeks after priming cycle (target: 4 weeks)
- Booster cycle 2: 4 to 12 weeks after booster cycle 1 (target: 4 weeks)
- Booster cycle 3: 4 to 12 weeks after booster cycle 2 (target: 4 weeks)

It is expected that a significant proportion of the patients will undergo adjuvant clinically indicated chemotherapy. Adjuvant chemotherapy can be administered between the courses of immunotherapy, but no sooner than 5 days after finishing any cycle of immunotherapy. The following cycle of immunotherapy will start no sooner than 5 days after the last day of a chemotherapy cycle and after recovery from acute side effect of chemotherapy.

Patients who (for clinical or logistic reasons) will not be able to take any cycle of immunotherapy within the above-indicated windows, can still receive the remaining courses of immunotherapy at later time points, but will not be included in the analysis of the primary efficacy endpoint, although they can be analyzed in an exploratory manner.

Similarly, patients who (for clinical or logistic reasons) will not be able to receive the priming dose of vaccine within 3 months after surgery, can still receive immunotherapy at later time points, but will not be included in the analysis of the primary efficacy endpoint, although they can be analyzed in an exploratory manner.

In the efficacy phase, patients will receive a priming dose of the α DC1 vaccine followed by 3 courses of the α DC1 booster vaccine combined with CKM regimen as illustrated in the following table:

Eligibility	Informed Consent CRS + HIPEC
Screening	History and physical exam, ECOG performance status, blood work, evaluation of tumor material
Post-surgery (within the first 8 weeks following surgery)	Leukapheresis
Week 1* (upon recovery from surgery; no sooner than 6 weeks post-surgery)	Priming Vaccine dose; no chemokine modulation) One day: α DC1 vaccine Oral celecoxib, 200 mg, before and after treatment on the day of vaccination
Weeks 2-3	Rest
Week 4 (target)*	Booster Cycle 1 Monday: α DC1 vaccine

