5.8 Off Study Treatment Visit

Within 1-2 weeks after the last day of study treatment, patients will have their last study specific clinical visit. At the discretion of the treating physician, the tests/procedures due to be performed at the Off Study Treatment visit may be performed on the last day of the CKM treatment for scheduling purposes.

AEs and conmeds will be collected for up to 5 days post last dose of treatment. Any patient experiencing study related SAE will be followed until resolution to Grade 1 or baseline.

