6. Peripheral blood for potential correlative studies will be collected at the following time points: once during the pre-screening, within 60 minutes before the vaccinations of the priming cycle, and booster cycles 1 and 2; and within 60 minutes after completing booster cycle 2 on Friday. Peripheral blood for potential correlative studies may additionally be drawn within 60 minutes before the vaccination of booster cycle 3 on Monday and within 60 minutes after completing booster cycles 1 and 3 on Friday.
7. Performed within 2 weeks prior to the priming dose of vaccine and 5 business days prior to cycles 1, 2 and 3 vaccines.
8. CT or MRI imaging should be performed prior to cycle 1 if the recovery period from surgery is greater than 6 weeks.
9. At the discretion of the treating physician, the tests/procedures due to be performed at the Off Study Treatment visit may be performed on the last day of the CKM treatment for scheduling purposes.
10. Performed as routine pre-operative evaluation.
11. AEs /conmeds should be collected up to 5 days after treatment, unless considered clinically significant or serious in nature in which case they will be followed until resolution or Grade 1.

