13.3 Data Analysis

At the completion of follow-up in evaluable patients, we will estimate progression-free survival by the Kaplan-Meier method with Greenwood 90% confidence intervals. We will conduct a formal test of the hypothesis that progression-free survival is improved with the experimental therapy. This test will be a one sided exponential test at $\alpha = .10$ that the median progression-free survival is better than 25% compared to historical controls. If this test is significant we will conclude that the progression-free survival is improved compared to the historical control. Descriptive summaries will be prepared of all adverse events by grade, frequency and attribution. An assessment of the association between immune parameters and survival will be conducted. The panel of immune parameters will be tested for association with progression-free and overall survival with Cox proportional hazards regression.

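### The secondary immune-marker analysis takes no account of adjuvant chemotherapy, which the protocol permits between compulsory blood samples and describes as able to change both immune response and outcome

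*Combined protocol and SAP*

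**What the plan says.** **Objective.** Section 1.2 sets out to "Perform correlative studies to characterize sequential immune response changes by quantitative measures of immune cellular phenotypes and chemokine patterns in peripheral blood". It relates these results to TTP, PFS and OS in search of predictive markers. Section 9 adds that such markers might later serve for patient selection or for decisions on continuing treatment.

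**Analysis.** Section 13.3 names one model: "The panel of immune parameters will be tested for association with progression-free and overall survival with Cox proportional hazards regression". Section 9 says TTP may be correlated with changes in the blood samples and leaves the scope of the work to clinical outcomes and funding. Neither section mentions chemotherapy in the analysis.

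**Chemotherapy as a cause.** Section 2.1 states: "Recent evidence indicates that chemotherapeutic agents can induce specific immune responses, thereby improving therapeutic outcomes". Of pleural mesothelioma it also reports that "patients receiving neoadjuvant chemotherapy with cisplatin/pemetrexed combination demonstrate higher CD8+ TILs than those receiving other chemotherapy regimens".

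**Chemotherapy in this trial.** Section 5.2: "It is expected that a significant proportion of the patients will undergo adjuvant clinically indicated chemotherapy". On timing, the same section says: "Adjuvant chemotherapy can be administered between the courses of immunotherapy, but no sooner than 5 days after finishing any cycle of immunotherapy". The next immunotherapy cycle may start 5 days after a chemotherapy cycle, once acute effects have resolved.

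**Samples.** Footnote 6 of the study calendar (section 10) makes five draws compulsory: one at pre-screening, three "within 60 minutes before the vaccinations of the priming cycle, and booster cycles 1 and 2", and one after booster cycle 2 on the Friday. Draws before booster 3 and after boosters 1 and 3 are optional.

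**The concern.** By the protocol's own account, chemotherapy can move both the marker and the outcome. It is expected to be common and is given at the treating oncologist's discretion. It can fall between two samples that a sequential analysis would compare. That makes it a candidate confounder, and with no control arm nothing else in the design separates its effect from that of vaccine plus CKM.

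Two readings are at risk. A change from before booster 1 to before booster 2 could be credited to the immunotherapy when chemotherapy produced it. A marker that only records who had chemotherapy could appear associated with progression or survival. The error can also run the other way and mask a genuine response. At stake is the credibility of markers that section 9 would consider carrying forward, not the primary efficacy conclusion.

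**Working it through.** **1. The plan's own figure.** No sample size or power is given for the immune analysis. The only sizing figure is 168 patients for the primary test, used here just as the number of patients. For a one-sided exponential test at 0.10 with 90% power, events = ((1.2816 + 1.2816)/ln 1.25)² = 132. With the case-mix mean historical median of 15.8 months, 36 months of accrual and 18 of follow-up, the event fraction is 0.771, so N = 132/0.771 ≈ 171, close to 168. Nothing below depends on this match.

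**2. Which contrasts can span chemotherapy.**

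| Contrast | Can chemotherapy fall inside it? |
|---|---|
| Pre-priming to pre-booster 1 | Yes under the Schema and the section 5.2 text; no if chemotherapy starts only after booster cycle 1 (section 5.2 table footnote; sections 6.2 and 7 read the same way) |
| Pre-booster 1 to pre-booster 2 | Yes under every reading |
| Baseline to post-booster 2 | Yes under every reading |
| Booster 2, Monday to Friday | No |

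**3. Cox marker model (the stated analysis).** Inputs from section 13.2: n = 168, tumour-type mix 15:40:60, medians 25/25/15 months, 36 months of uniform accrual plus 18 of follow-up. Assumptions: 30% or 50% have chemotherapy before the sample; it shifts the marker by 0.5–1.0 SD; its hazard ratio is 0.6–0.8; the marker has no effect of its own. With 3,000 simulated trials per setting and a two-sided 5% score test stratified by tumour type, the null marker is flagged about 5–20% of the time. Adding chemotherapy as a stratum brings this to about 5%.

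A simpler separate simulation, without tumour types and with an 18-month median in the unexposed, gives (unadjusted / stratified by chemotherapy):

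| Exposed | Shift (SD) | HR 0.8 | HR 0.67 |
|---|---|---|---|
| 30% | 0.5 | 5.6% / 5.0% | 7.1% / 4.8% |
| 30% | 1.0 | 6.6% / 4.8% | 12.8% / 5.6% |
| 50% | 0.5 | 6.1% / 5.3% | 8.1% / 5.2% |
| 50% | 1.0 | 8.7% / 4.9% | 16.0% / 5.7% |

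With HR 1.0, the unadjusted rate stays at 5–6%.

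**4. Between-cycle change.** The plan specifies no test of this change. Suppose it were tested against zero across all patients. With share p exposed and shift d, the mean change is p·d and its SD is √(1 + p(1−p)d²); z = p·d·√n/SD, and the chance of significance at two-sided 5% is about Φ(z − 1.96).

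- p = 0.3, d = 0.5, n = 168: mean 0.15, SD √1.0525 = 1.026, z = 0.15 × 12.96/1.026 = 1.895, chance 47%.
- p = 0.5, d = 1.0, n = 168: mean 0.50, SD √1.25 = 1.118, z = 5.80, chance over 99%.
- The same two settings with n = 100: 31% and 99%.
- p = 0.3, d = 0.2, n = 168: mean 0.06, z = 0.77, chance 12% (including the small opposite tail).

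With a chemotherapy term, simulation gives about 5% for d = 0.2 and 0.5. Masking is the same arithmetic with the sign reversed: a shift of −0.5 SD in 30% of patients gives 0.3 × (−0.5) = −0.15 SD, enough to cancel a true mean response of +0.15 SD.

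**The case against.** **No pooled test is written down.** A reader might infer that sections 9 and 13.3 pool all patients and intervals. They do not say so; they are silent on chemotherapy, and the only named model is Cox. The 47% to over 99% range therefore belongs to a hypothetical test. This stands.

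**The Cox inflation is modest.** It needs three assumed inputs and is close to nominal at the weak end. Sections 2.1 and 2.3 describe minimal benefit from systemic chemotherapy in mesothelioma and appendiceal disease, which make up 15 + 40 = 55 of the 115 cases expected per year. A hazard ratio of 0.6–0.8 in every patient may be too strong. This also stands.

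**The immune premise is indirect.** Section 2.1 says chemotherapy *can* induce responses and relies on a murine model and tumour-cell sensitisation. Section 2.2 cites a pilot with stable levels of peripheral blood mononuclear cells during adjuvant chemotherapy. That weakens the assumed shift without removing it, because stable cell levels do not establish stable phenotype or chemokine patterns.

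**Recording.** Section 5.8 says "AEs and conmeds will be collected for up to 5 days post last dose of treatment". A reader might infer that the chemotherapy that matters goes unrecorded. It does not follow: the calendar collects concomitant medication at every cycle visit, and chemotherapy between samples precedes the last dose. Chemotherapy after the last sample cannot move a marker already drawn. What remains is that no item asks specifically for regimen and dates.

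**Secondary and exploratory.** The correlative scope is open, and section 9's later uses are only possibilities. That limits the severity; it does not make the unadjusted model preferable.

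**Conclusion.** The point holds as a risk of misattribution in the secondary immune analysis. The Cox model run as written can flag a marker that only records chemotherapy exposure, and at least one pair of compulsory samples spans a permitted chemotherapy window under every reading of the protocol.

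The documents do not support the stronger claim that a chemotherapy effect *will* be reported as a vaccine response. That depends on the chemotherapy share, the marker shift and the hazard ratio, none of which they give. Over the assumed ranges, the false-positive rate of the stated model is about 5–20%, against about 5% with a chemotherapy stratum. If chemotherapy affects only the marker or only the outcome, the Cox error stays near 5%; a between-cycle change, however, is vulnerable to a marker effect alone. The simulations treat chemotherapy as yes/no and as the only confounder, so the return to 5% is a best case.

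This is worth changing before analysis. The primary test is not affected.

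**What to change.** In sections 9 and 13.3:

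1. Stratify or adjust the marker Cox models for chemotherapy received before the sample, alongside tumour type, and count follow-up from the sample date.
2. Report between-cycle marker changes separately for intervals with and without chemotherapy.
3. Report the booster 2 Monday-to-Friday change as a supporting measure. Both samples are already compulsory and no chemotherapy can fall between them. State that it reflects acute CKM exposure and possible carry-over from recent chemotherapy, and does not replace the sequential changes the objective targets.
4. Capture chemotherapy regimen and dates up to the last sample, from the concomitant-medication visits and the medical records already used for follow-up.

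Separately, reconcile the passages on when chemotherapy may start (Schema and section 5.2 text against the section 5.2 table footnote and sections 6.2 and 7). They decide whether the pre-booster 1 sample is free of between-cycle chemotherapy.

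The cost is analysis-plan wording and a case-report-form entry, with no extra blood draws or patients. The downside is slightly less precision in the split analyses.
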